### 8.2.7. Efficacy Analysis

- **Response rate and clinical benefit rate**

The number and percentage of patients by best overall response, the response rate and its 95% confidence interval, and the clinical benefit rate and its 95% confidence interval will be tabulated in the safety analysis set and efficacy analysis set.

The response rate is defined as the percentage of patients whose best overall response is CR or PR.

The clinical benefit rate is defined as the percentage of patients whose best overall response is CR, PR, or SD.

The best overall response is defined as the best response among recorded overall response.

Table 1 of “New Guideline for the Assessment of Treatment Effect on Solid Cancer (Response Evaluation Criteria in Solid Tumors [RECIST] Guideline)–Japan Clinical Oncology Group [JCOG] version in Japanese” will be used for overall response, but overall response based on combinations of tumor response not corresponding to the table because of unknown data and no entry of data was uniquely defined. Therefore, the

tabulation analysis is not in complete compliance with the guideline and uses the guideline for reference.

**Table 1. Overall Response Based on Combinations of Tumor Response in Target and Non-target Lesions Including the Presence or Absence of New Lesions**

Target lesion	Non-target lesion	New lesion	Overall response
HCR	CR	Absent	CR
CR	IR/SD	Absent	PR
PR	Other than PD	Absent	PR
SD	Other than PD	Absent	SD
PD	Any response	Any response	PD
Any response	PD	Any response	PD
Any response	Any response	Present	PD

The following tumor response will be converted as shown by the arrow.

Non-target lesion: Absent → CR, not entered → IR/SD.

New lesion: Not entered → absent.

Overall response not corresponding to any combination in Table 1 after the above conversion will be considered as “unassessable.”

In addition, tabulation will be performed in the same manner by category shown below.

For items using reference laboratory test values, results using corporate reference values will be tabulated separately from results using institutional reference values as necessary.

- Site of metastasis [none, lung, liver, bone, lung + 1 organ, lung + 2 organs, lung +  $\geq 3$  organs,  $\geq 2$  organs other than lung, others];
- Whether criteria for proper use are met [yes, no];

- Prior treatment history [IFN- $\alpha$ , IL-2, Sutent, Nexavar, Afinitor, others];
- Baseline LDH (1.5-fold of institutional upper reference limit) [high value ( $>1.5$ -fold), normal ( $\leq 1.5$ -fold)];
- Baseline LDH (1.0-fold of institutional upper reference limit) [high value ( $>1.0$ -fold), normal ( $\leq 1.0$ -fold)].

In addition, the above tabulation will be performed using the best overall response as a study not requiring determination of CR and PD.

- Response rate and clinical benefit rate by patient demographic

The response rate and clinical benefit rate will be calculated by item listed in “[Section 10.1.1. Patient demographics to be used to evaluate safety and efficacy.](#)” For the response rate and clinical benefit rate, tests specified in [Section 8.1.3](#) will be performed between categories of each demographic factor.

For items using reference laboratory test values, results using corporate reference values will be tabulated in addition to results using institutional reference values.

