5.4 Observation period

The observation period for this study will be set until Week 24 after the start of administration (cases treated with the drug for more than 25 weeks will be included in the separately planned Special Investigation on long-term use and observed for up to 96 weeks after the start of administration)

[figure not shown]
Clinical evaluation of tumor: Weeks 8, 16, and 24. For discontinued cases, if the clinical evaluation of tumor is not performed within 4 weeks prior to discontinuation, clinical evaluation of tumor will be performed at the time of discontinuation.

Adverse events: Until Week 24 after the start of administration. If the drug is discontinued before Week 24, observe until Day 28 after the discontinuation of administration.

This study will be conducted using a case report form divided into separate booklets. The results during the following observation periods will be recorded in the different booklets of the case report form.

| Booklet | Observation period |
|------------|---|
| Booklet 01 | Start of administration to Week 4 (Day 28) |
| Booklet 02 | Week 5 (Day 29) to Week 12 (Day 84) after start of administration |
| Booklet 03 | Week 13 (Day 85) to Week 24 (Day 168) after start of administration |

(Start of administration)
(Day 1)

Observation period and evaluation time points for each booklet of case report form

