7.2.2 Analysis for effectiveness evaluation

The response rate and clinical benefit rate as shown below will be used as main analytical items in the effectiveness analysis set. An **CCI** analysis including the examination of factors influencing effectiveness will be performed, as required.

- [1] Response rate (rate of CR + PR)
- [2] Clinical benefit rate (Rate of cases with CR + PR + SD maintained for 24 weeks or longer)

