## 6.2. Efficacy Endpoints

1. Response rate (percentage of complete response [CR] + partial response [PR])
2. Clinical benefit rate (percentage of CR + PR + stable disease [SD] for at least 24 weeks)
3. Progression-free survival (PFS): Time from the date of initiation of treatment with this drug in this study to the date progressive disease (PD) or all-causality death is first confirmed during the treatment period (including 28 days after the completion of treatment with this drug) and the period up to the date of final evaluation of tumor response. PD or death occurring during the treatment period (including 28 days after the completion of treatment with this drug) or the period up to the date of final evaluation of tumor response, whichever period is the earlier, will be handled as a PFS event, and patients without a PFS event will be censored at the date of final evaluation of tumor response. Patients with no record on tumor response at all will be censored at the date of initiation of treatment with this drug.

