### **8.2. Statistical Analyses**

Unless otherwise specified, data from the all patient surveillance and data from the long-term use surveillance will be tabulated and analyzed together.

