- List of patients with skin disorder [major investigation].
- List of patients with acute renal failure [major investigation].
- List of patients with gastrointestinal perforation [major investigation].

- List of tumor response.
- List of whether criteria for proper use are met.
- List of whether criteria for proper use are met (corporate reference values are used as reference laboratory test values).
- List of chest CT.

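### SAP 8.2.7 counts stable disease of any duration as clinical benefit, while protocol 7.2.2 and SAP 6.2 require at least 24 weeks, so the reported rate can only be equal to or higher than the defined one

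*SAP*

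**What the plan says.** Three places in the current text define the same named rate.

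- Protocol 7.2.2, among the main effectiveness items: "Clinical benefit rate (Rate of cases with CR + PR + SD maintained for 24 weeks or longer".
- SAP 6.2, Efficacy Endpoints: "Clinical benefit rate (percentage of CR + PR + stable disease [SD] for at least 24 weeks".
- SAP 8.2.7, Efficacy Analysis: "The clinical benefit rate is defined as the percentage of patients whose best overall response is CR, PR, or SD".

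SAP 8.2.7 then adds: "The best overall response is defined as the best response among recorded overall response". Its Table 1 assigns SD at an evaluation from the target-lesion, non-target-lesion and new-lesion findings, without reference to time. Protocol 6.5.1 schedules tumor evaluations at Weeks 8, 16 and 24.

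The rate and its exact 95% confidence interval are tabulated in the safety and efficacy analysis sets and broken down by several categories. The by-demographic paragraph of 8.2.7 carries the rate further: "The response rate and clinical benefit rate will be calculated by item listed in" SAP 10.1.1, with tests between categories.

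**The concern.** The SAP defines its endpoint one way in section 6 and derives it another way in section 8. The wording in 8.2.7 is framed as a definition and can be programmed without consulting 6.2. No visible text in 8.2.7 brings back the 24-week condition or says which section governs.

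If 8.2.7 is followed, the headline rate, its confidence interval, the breakdowns and the by-demographic tests all carry the protocol's endpoint name but measure something looser. The final analysis supports the re-examination application (SAP 3), so the mislabelled figure would go into that submission. A reader could see that the rate equals CR + PR + SD in the best-response table. That table gives no SD durations, so the reader could not recover the rate the protocol defines.

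**Working it through.** The documents state no expected clinical benefit rate, so there is no planned figure to reproduce. The check covers the logic, the direction of the difference, and what can be said about its size.

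**1. The definitions side by side**

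| Patient's evaluations | Protocol 7.2.2 / SAP 6.2 | SAP 8.2.7 |
|---|---|---|
| Best response CR or PR | benefit | benefit |
| SD at Weeks 8, 16 and 24 (duration counted from first dose) | benefit | benefit |
| SD at Week 8, PD at Week 16 | no benefit | benefit |
| PD at the first evaluation, nothing better later | no benefit | no benefit |

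Only the third row differs, and it differs in one direction.

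**2. Direction**

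Patients with CR, PR or SD of at least 24 weeks are a subset of patients with a best response of CR, PR or SD. To confirm this, every response sequence was enumerated over four evaluations (Weeks 8, 16, 24 and an assumed Week 32), each with five outcomes (CR, PR, SD, PD, not evaluable). SD was taken to last from the start of treatment to the last evaluation without progression.

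- Number of sequences: 5^4 = 625.
- Meeting the 24-week rule but not 8.2.7: 0. This also holds if the 24 weeks are read as qualifying CR and PR as well as SD.
- Meeting 8.2.7 but not the 24-week rule (condition on SD only): 49. Sequences with best response SD number 3^4 − 2^4 = 65. Of these, 16 reach Week 24 or later without progression, and 65 − 16 = 49.

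On the same analysis set, the 8.2.7 rate is therefore always equal or higher.

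**3. Size**

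Gap = (patients with best response SD lasting under 24 weeks) / N.

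- N = 600 (the target in protocol 3): 1/600 = 0.17 percentage points per patient.
- N = 300 (assumed): 1/300 = 0.33 points per patient.

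The documents give neither an SD rate nor SD durations. As an illustration, assume best response SD in 40–60% of patients, with 20–50% of those lasting at least 24 weeks. The gap is SD share × (1 − long-lasting share), which runs from 0.40 × 0.50 = 20 points to 0.60 × 0.80 = 48 points. If every SD lasts 24 weeks, the gap is 0.

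**4. How few patients would matter**

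The table shows the smallest number of short-SD patients that puts the 24-week rate below the exact (Clopper-Pearson) 95% lower limit around the 8.2.7 rate. The N values and rates are assumed.

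| 8.2.7 result | Lower limit | Short-SD patients needed |
|---|---|---|
| 90/300 | 24.9% | 16 |
| 150/300 | 44.2% | 18 |
| 210/300 | 64.5% | 17 |
| 180/600 | 26.4% | 22 |
| 300/600 | 45.9% | 25 |
| 420/600 | 66.2% | 24 |

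For example, (150 − 18)/300 = 44.0%, below 44.2%, while (150 − 17)/300 = 44.3% is not. This gives a sense of scale only. It neither estimates the gap nor tests the difference.

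**The case against.** The strongest reply is that little hangs on this rate. SAP 4 says the study is not confirmatory, the visible plan attaches no decision rule to clinical benefit, and protocol 3 sizes the study on adverse events. The response rate and progression-free survival are unaffected. The patient who has SD at Week 8 and progresses at Week 16 would ordinarily appear as a PFS event. All of that is true, and it limits the consequences. It does not allow one named endpoint to have two definitions, and neither PFS nor the best-response table supplies the 24-week rate.

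A second reply is that the rule actually programmed is uncertain. SAP 8.2.7 describes a further tabulation on a basis that does not require CR and PD to be determined. Its wording is unclear, and some SAP text is redacted or was not available for this review. That is a fair caution about what will be done. The visible description of that tabulation mentions no SD duration, and the conflict between 6.2 and 8.2.7 stands on the current text.

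A third reply is that patient-level data will be listed. SAP 9 promises only a "List of tumor response" and does not give its contents, so it might or might not allow the defined rate to be derived.

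The illustrations of size rest wholly on assumed rates, and the conclusion does not depend on them.

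**Conclusion.** The concern holds, and the plan needs correcting. As written, SAP 8.2.7 does not compute the clinical benefit rate defined in SAP 6.2 and protocol 7.2.2. The 8.2.7 rate is equal to the defined rate or higher. They are equal only if no patient's best response is SD lasting under 24 weeks. This direction needs no data; it assumes only the same analysis set and the same derivation of overall response at each evaluation. The size of the gap cannot be determined from the documents.

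**What to change.** In SAP 8.2.7, define clinical benefit as a best overall response of CR or PR, or SD documented as lasting at least 24 weeks. Use that definition for the headline rate, its confidence interval, the breakdowns and the by-demographic tests. Three details need to be stated:

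1. **Start of the SD clock and day count.** If SD were timed from its first record at Week 8, the Week 24 evaluation would give only 24 − 8 = 16 weeks, so the choice of start is decisive. If it is timed from first dose, note that protocol 5.4 labels Week 24 as Day 168 with Day 1 as the start. Date subtraction then gives 168 − 1 = 167 days, whereas an inclusive count gives 168 = 24 × 7. This is minor but should be settled.
2. **A window around Week 24, and use of later evaluations.** SAP 8.2 says "data from the all patient surveillance and data from the long-term use surveillance will be tabulated and analyzed together", and protocol 5.4 has long-term patients "observed for up to 96 weeks after the start of administration". The long-term objective in SAP 2.2.2 is safety, however, and the documents do not show whether tumor evaluations continue after Week 24.
3. **A rule for SD patients with no evaluation at or after 24 weeks.** SAP 7 provides no missing-data rule. One option is to count them as no benefit, by analogy with the handling of unassessable patients in the safety set described in the version 3.0 entry of SAP 1. A sensitivity analysis would then treat them as unassessable.

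If CR + PR + SD of any duration is also of interest, report it separately under a different name, such as disease control rate.

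The cost is one revised definition, one derivation reprogrammed from recorded evaluations, and one sensitivity table, provided the recorded evaluations suffice to measure 24 weeks. The reported rate will be equal or lower. Under the no-benefit option, patients who stop early for reasons other than progression count against the drug.

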6.5 Effectiveness evaluation

6.5.1 Clinical evaluation of tumor

Clinical evaluation of tumor will be performed at Weeks 8, 16, and 24 after the start of administration. The presence/absence of the target, non-target, and new lesions will be evaluated at each evaluation time point. The evaluation will be performed using the following 4 classes with reference to the "New response evaluation criteria in solid tumours: Revised RECIST guideline (version 1.1) - Japanese Translation JCOG Version."

| | | |
|---------------------|------|---|
| Complete response | (CR) | Disappearance of all target regions |
| Partial response | (PR) | At least a 30% decrease in the sum of the longest diameter (LD) of target lesions, taking as reference the baseline sum LD |
| Progressive disease | (PD) | At least a 20% increase in the sum of the LD of target lesions, taking as reference the smallest sum LD recorded since the treatment started |
| Stable disease | (SD) | Neither sufficient shrinkage to qualify for PR nor sufficient increase to qualify for PD, taking as reference the smallest sum LD since the treatment started |

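### Best overall response has no cut-off at first progression, so a patient who is already a PFS event can still be counted as a responder or as clinical benefit

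*SAP*

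**What the plan says.** SAP 8.2.7 builds both main effectiveness rates on one derived variable. Its definition is: "The best overall response is defined as the best response among recorded overall response". Two rules follow from it: "The response rate is defined as the percentage of patients whose best overall response is CR or PR" and "The clinical benefit rate is defined as the percentage of patients whose best overall response is CR, PR, or SD".

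The overall response at each evaluation comes from Table 1 of SAP 8.2.7, which combines target, non-target and new lesions. Before the table is applied, a new-lesion field left blank is converted to absent. No rule carries an earlier new lesion forward. The SAP says that it uses the response guideline for reference and does not fully comply with it.

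SAP 6.2 dates a PFS event at "the date progressive disease (PD) or all-causality death is first confirmed during the treatment period" (the window extends to 28 days after treatment and is also bounded by the last tumor evaluation). There, the first PD settles the patient's status.

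On timing, Protocol 6.5.1 says: "Clinical evaluation of tumor will be performed at Weeks 8, 16, and 24 after the start of administration". For discontinued cases, Protocol 5.4 asks for an evaluation at discontinuation if none was done in the preceding 4 weeks. Neither document ends tumor evaluation at PD or discards records made after it.

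**The concern.** Protocol 7.2.2 names the response rate and clinical benefit rate as the main effectiveness items. SAP 8.2.7 also tests them across demographic factors. If a record made after progression can set the best response, these rates can credit the drug with benefit in patients whom the PFS analysis already counts as failures. The two results would then be reported side by side with PD handled in incompatible ways. The best of a longer list cannot be worse than the best of a shorter one, so the discrepancy can only raise the rates.

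**Working it through.** The plan states no figure for this point, so there is none to reproduce. The check applies the written rules.

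**One patient through Table 1.**
- Week 8: target SD, new lesion present. The last row of Table 1 gives PD, which is a PFS event at Week 8.
- Week 16: target SD, non-target field blank (converted to IR/SD), new-lesion field blank (converted to absent). The SD row gives SD.
- Best overall response as written is SD, so the patient counts as clinical benefit under 8.2.7. With target PR at Week 16, the result is PR and the patient is a responder.

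**All possible sequences.** With four responses at Weeks 8, 16 and 24 there are 4³ = 64 sequences, of which 64 − 3³ = 37 contain a PD. For each, compare the best of all records with the best up to and including first PD.

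| First PD at | Sequences | Non-PD record after PD | Best response improves | Becomes responder only after PD | Gains 8.2.7 clinical benefit only after PD |
|---|---|---|---|---|---|
| Week 8 | 4×4 = 16 | 16−1 = 15 | 15 | 16−2×2 = 12 | 15 |
| Week 16 | 3×4 = 12 | 3×3 = 9 | 3 | 2 | 0 |
| Week 24 | 3×3 = 9 | 0 | 0 | 0 | 0 |
| Total | 37 | 24 | 18 | 14 | 15 |

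The three improving sequences with first PD at Week 16 are SD-PD-PR, SD-PD-CR and PR-PD-CR. Only the first two create a new responder.

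Examples: PD-PR-PR moves from PR to PD once the cut-off is applied, PD-SD-SD from SD to PD, and SD-PD-PR from PR to SD. With the cut-off, the last three totals are all 0. These are counts of logical possibilities, not expected patient frequencies.

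**Who is affected.** Of the 24 sequences with a non-PD record after first PD, only 15 gain clinical benefit. The other 9 already have CR, PR or SD before PD and count either way. Similarly, the response rate changes only where no CR or PR precedes the PD.

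**Dependence on the clinical benefit definition.** SAP 6.2 and Protocol 7.2.2 require SD to last at least 24 weeks, a condition that 8.2.7 drops. If the 6.2 rule is read as SD at all three visits, the clinical benefit count falls from 15 to 14, and all 14 arise through a CR or PR after PD. Late SD therefore matters under the 8.2.7 rule, and late CR or PR under both. The conflict between the two definitions needs its own reconciliation.

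**Size.** If a fraction f of the analysis set is reclassified, the rate rises by f. As an illustration only, assume 300 evaluable patients, a true response rate of 10% and f from 1% to 5%:
- f = 0: 30/300 = 10%, exact 95% CI 6.9% to 14.0%
- f = 1%: 33/300 = 11%, exact 95% CI 7.7% to 15.1%
- f = 5%: 45/300 = 15%, exact 95% CI 11.2% to 19.6%

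All three inputs are assumptions. The documents give no rate of non-PD records after PD.

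**The case against.** The strongest reply is that such records should be scarce. Protocol 6.7 lists insufficient effectiveness as a reason for discontinuation. Protocol 3 assumes that only 50% of patients continue to 12 weeks, and SAP 2.1.2 expects only 20% to be registered in the long-term surveillance after 24 weeks. Protocol 6.5.1 judges both PD and SD against the smallest sum of diameters, so a target-lesion PD does not revert to SD without real shrinkage. It also asks for the presence or absence of new lesions to be evaluated every time, so the blank-field route needs an incomplete form. SAP section 4 says that the study is not confirmatory. All of this stands and limits the likely size, but none of it makes the rule stop at PD.

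It can also be argued that the guideline supplies the cut-off and that the SAP departs from it only for unknown or unentered data. The guideline is not among the documents, and the SAP takes it for reference only. The explicit sentence in 8.2.7 is what a programmer will follow.

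Three stronger readings are tempting, and the documents do not support them:
- A reader might infer that the search runs to 96 weeks, because under SAP 8.2 "data from the all patient surveillance and data from the long-term use surveillance will be tabulated and analyzed together". Tumor evaluation is specified only to Week 24, the stated long-term objective is safety, and neither document shows that tumor response is collected later.
- A reader might infer that every patient with a non-PD record after PD inflates clinical benefit. Those with SD or better before PD do not (9 of the 24 sequences above).
- A reader might infer that the further tabulation merely repeats the main one, because the main definition has no confirmation step. The text is: "the above tabulation will be performed using the best overall response as a study not requiring determination of CR and PD". Its meaning is unclear, and duplication follows only if confirmation is meant, which the SAP does not say.

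**Conclusion.** The point holds. As written, the best-response rule in SAP 8.2.7 lets records after first PD decide the response rate and the clinical benefit rate, while SAP 6.2 treats that PD as a PFS event. The direction is certain: the rates are unchanged or too high. The size is 1 percentage point for each 1% of patients reclassified, confined to patients with no CR or PR before PD (response rate) or no CR, PR or SD before PD (clinical benefit under 8.2.7). How many such patients there are cannot be derived from the documents. The number may be small if most patients stop treatment at PD. The conclusion rests on reading the 8.2.7 sentence literally, and no other provision in the documents restricts it. It is worth correcting because these are the protocol's main effectiveness items and the correction is simple.

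**What to change.** In SAP 8.2.7, define best overall response as the best overall response recorded from the start of treatment up to and including the first PD, and state that later records are not used. Apply the same derivation to the tabulations and tests by patient factor. With this cut-off, a blank new-lesion field after PD can no longer affect the result.

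Separately, state what the further tabulation of best overall response is meant to show and how its derivation differs from the main one.

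The cost is one sentence and one filter in the derivation, with no new data. The reported rates may fall slightly.

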## **5.2. Efficacy Analysis Set**

The efficacy analysis set basically consists of evaluable patients (patients considered to have undergone an appropriate evaluation).

However, patients who violate efficacy criteria among separately specified patient inclusion criteria will be excluded.

Not meeting conditions for target patients, experience of treatment with this drug, efficacy evaluation “unassessable” (not meeting conditions for assessment).

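### SAP 8.2.7 gives no conversion for an unknown non-target lesion, so a target-lesion CR with that entry is unassessable while a blank entry gives PR

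*SAP*

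**What the plan says.** SAP 8.2.7 derives overall response at each evaluation from Table 1, which combines target, non-target and new-lesion status. It says that overall response for combinations "not corresponding to the table because of unknown data and no entry of data was uniquely defined". Two conversions follow: "Non-target lesion: Absent → CR, not entered → IR/SD" and "New lesion: Not entered → absent". Then comes a residual rule: "Overall response not corresponding to any combination in Table 1 after the above conversion will be considered as" unassessable.

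In Table 1 the target CR rows name their non-target states: CR gives overall CR, and IR/SD gives overall PR. The target PR and target SD rows instead accept every non-target status except PD.

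For the summary measures, "The response rate is defined as the percentage of patients whose best overall response is CR or PR". Clinical benefit in the same section adds SD. "The best overall response is defined as the best response among recorded overall response". Protocol 6.5.1 sets the evaluation times: "Clinical evaluation of tumor will be performed at Weeks 8, 16, and 24 after the start of administration".

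SAP 5.2 says of the efficacy set: "However, patients who violate efficacy criteria among separately specified patient inclusion criteria will be excluded". The list below that sentence includes an unassessable efficacy evaluation. SAP 8.2.7 tabulates both rates in the safety set as well. The version 3.0 entry in SAP section 1 explains that this analysis counts unassessable patients as not having responded or benefited.

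**The concern.** The plan names two kinds of incomplete entry and gives a rule for only one of them. For a patient whose target lesions have all disappeared, the score then depends on whether the site left the non-target field empty or recorded it as unknown. Neither entry tells the analyst anything about the non-target lesions, yet one gives PR and the other gives no response at all. On the literal wording of the PR and SD rows, the same unknown entry does no harm to a patient with a lesser target response.

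Both main effectiveness items, response rate and clinical benefit rate, use this derivation. A programmer who follows the text literally and one who treats unknown like blank would report different rates from the same data.

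**Working it through.** **Inputs.** Table 1, the conversions and the residual rule come from SAP 8.2.7. The evaluation times come from Protocol 6.5.1, and the analysis-set rules from SAP 5.2 and the version 3.0 entry in SAP section 1. The target entry in the first row of Table 1 is read as CR; the garbled label does not affect the result. The plan gives no figure on this point to reproduce.

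**Step 1: apply the rules as written, new lesion absent or not entered.**

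| Target | Non-target CR or absent | Non-target IR/SD or not entered | Non-target unknown | Non-target PD |
|---|---|---|---|---|
| CR | CR | PR | **unassessable** | PD |
| PR | PR | PR | PR* | PD |
| SD | SD | SD | SD* | PD |
| PD | PD | PD | PD | PD |

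*If the condition in these rows (anything but PD) is taken to include unknown.

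Among target responses of CR, PR, SD or PD, target CR with non-target unknown is the only cell here that becomes unassessable.

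**Step 2: two comparisons.**

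- Within the target CR rows, blank gives PR and unknown gives unassessable. This does not depend on how the PR and SD rows are read.
- Across rows with non-target unknown, CR gives unassessable, PR gives PR and SD gives SD. This depends on the starred reading.

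**Step 3: from evaluation to patient.** Best overall response is the best one recorded.

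- CR or PR at any other evaluation: the patient remains a responder and nothing is lost.
- SD as the best other result: lost from the response rate, kept in the clinical benefit rate.
- Only PD elsewhere: lost from both rates, but stays in the efficacy-set denominator.
- No other assessable evaluation: leaves the efficacy set and counts as a failure in the safety set.

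With r responders among n patients, of whom k are affected, the safety-set rate falls from r/n to (r − k)/n. If all k also leave the efficacy set, that rate falls from r/n to (r − k)/(n − k), which is below r/n whenever r < n. So, compared with scoring the cell as PR, the direction is downward in both sets.

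**Step 4: size, on assumptions only.** Suppose target CR occurs in 1–3% of patients and the non-target entry is unknown in 10–30% of those. Then 0.01 × 0.10 = 0.1% and 0.03 × 0.30 = 0.9%. Of the planned 600 patients, that is 0.6 to 5.4. Against an assumed 10% response rate, it is 0.1/10 = 1% to 0.9/10 = 9% of responders. No allowance is made for CR or PR at another evaluation, so each figure is an upper bound for its inputs.

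Assume 60 true responders, 600 patients in the safety set and 500 in the efficacy set:

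| k | Safety set | Efficacy set |
|---|---|---|
| 0 | 60/600 = 10.0% | 60/500 = 12.0% |
| 1 | 59/600 = 9.8% | 59/499 = 11.8% |
| 3 | 57/600 = 9.5% | 57/497 = 11.5% |
| 6 | 54/600 = 9.0% | 54/494 = 10.9% |

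The exact 95% interval for the safety set is 7.7–12.7% at k = 0 and 6.8–11.6% at k = 6. The shift is small against the width of the interval.

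**Step 5: apply the fix.** Converting non-target unknown to IR/SD turns the bold cell into PR. No other cell in the step 1 table changes.

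**The case against.** A reader might infer that the plan penalises the best responders: a better tumour response takes the patient out of the numerator, and the response rate is biased as a result. The documents do not support that much, for five reasons.

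- Loss is not automatic. The label applies to one evaluation, and any other CR or PR keeps the patient a responder. This stands.
- The reversal between target CR and target PR needs the PR row to admit unknown. The SAP's own sentence about unknown data putting combinations outside the table can be read the other way, and then PR and SD with unknown are unassessable too. This stands as an ambiguity. It does not remove the blank-versus-unknown difference under target CR.
- The case report form options are not in the documents. That a non-target lesion can be recorded as unknown is inferred from the SAP naming unknown data apart from missing entries. If the form has no such option, the cell is empty.
- Unknown entries affect more than complete responders. An unknown new-lesion entry is not converted either, and it makes target CR, PR and SD alike unassessable unless another entry already gives PD. That loss does not depend on how good the target response is.
- An unknown non-target status could hide progression, so calling it unassessable might be deliberate caution. But the plan accepts the same risk for a blank entry under target CR and, on its wording, for unknown in the PR and SD rows. Making unknown unassessable in every row would be uniform, but it would still leave blank and unknown scored differently.

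The SAP also says its tests are not confirmatory and that its tabulation does not fully follow the response guideline. Both points limit the consequence. Neither explains why two uninformative entries are scored differently.

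**Conclusion.** The point holds as an internal inconsistency of minor severity. Under the stated rules, target CR with an unknown non-target status and no new lesion is unassessable, while the same patient with a blank field is PR. On the literal wording, target PR or SD with unknown also keeps its score. Compared with scoring the cell as PR, the effect on the response and clinical benefit rates can only be downward.

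The size cannot be derived from the documents. The 0.1 to 0.9 percentage points rest wholly on assumed frequencies and leave out rescue by other evaluations, so the real effect is probably small. Two further steps are inferred: that unknown is a possible non-target entry, and that the patient-level exclusion in SAP 5.2, whose criteria are specified elsewhere, applies when every evaluation carries the Table 1 label. The documents do not show a materially biased response rate.

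**What to change.** Add unknown → IR/SD to the non-target conversion in SAP 8.2.7. Equivalently, widen the second row of Table 1 to any non-target status that is neither CR nor PD, with unknown named. Target CR with unknown and no new lesion then gives PR. State as well that the non-target condition in the PR and SD rows includes unknown. The conversion already implies this; the widened row does not, so the statement is needed in that case.

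The cost is a line or two of SAP text, one line of derivation code and no new data. The downside is that an unknown status could conceal progression, a risk the plan already takes for blank entries. Reporting how many evaluations have target CR with an unknown non-target status would replace the assumed size with an actual count.
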